will return twice for testing, first on the day after irradiation and second the following day. At each testing session the area of UV radiation will be heated to 40°C twice separated by 40 minutes.

RANDOMIZED TREATMENT

We propose to take advantage of the stable nature of this model of peripheral injury for 2-3 days in order to apply a randomized, blinded, cross over design with treatment with oxytocin one day and placebo on another. Following baseline measures on each of the two study days, subjects will receive an intramuscular injection of oxytocin (Pitocin®) in its indicated dose of 10 IU (17 µg) or an equivalent volume of saline. In the absence of pregnancy or the postpartum period, doses of oxytocin much greater than this (24-80 IU) produces no physiologic adverse effects when administered intranasally, which produces rapid systemic absorption [15; 17; 21; 27; 32].

RATIONALE FOR PRIMARY OUTCOME MEASURES AND TIMING OF MEASUREMENTS

We will determine thresholds to perception of vibration at a frequency of 256 Hz, pain within the area of UV burn, and area of hypersensitivity to von Frey filament testing before and at the following times after intramuscular study drug injection: 5 minutes, 45 minutes, and 65 minutes. We will also perform a vibration threshold at 30 minutes after the intramuscular injection. These primary outcome measures will assess both A β and A δ /C fiber sensitivity in the area of injury and these times will capture the time of peak plasma oxytocin concentration after intramuscular injection [20].

TEST OF A β FIBER SENSITIVITY

Light touch is subserved by a group of myelinated peripheral nerves with fast conduction in the A β range and which are capable of following high frequencies, being responsible for the sensation of vibration. This capability of individual nerve fibers to respond with high frequency also underlies our ability to sense a light touch moving across the body surface as in brushing.

As noted, preclinical studies show that following injury these light touch fibers become less sensitive to repeated stimulation as occurs with a vibration [2]. Oxytocin,

when perfused around the neuronal cell bodies of these A β nerve fibers, partially restores their function, including their sensitivity to low intensity stimulation.

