3. Normal blood pressure (systolic 90-140 mmHg; diastolic 50-90 mmHg) resting heart rate 45-100 beats per minute) without medication
4. Female subjects of child-bearing potential and those < 1 year post-menopausal, must be practicing highly effective methods of birth control such as hormonal methods (e.g., combined oral, implantable, injectable, or transdermal contraceptives), double

barrier methods (e.g., condoms, sponge, diaphragm, or vaginal ring plus spermicidal jellies or cream), or total abstinence from heterosexual intercourse for a minimum of 1 full cycle before study drug administration.

Exclusion Criteria:

1. Hypersensitivity, allergy, or significant reaction to any ingredient of Pitocin®
2. Any disease, diagnosis, or condition (medical or surgical) that, in the opinion of the Principal Investigator, would place the subject at increased risk (active gynecologic disease in which increased tone would be detrimental e.g., uterine fibroids with ongoing bleeding), compromise the subject's compliance with study procedures, or compromise the quality of the data
3. Women who are pregnant (positive result for urine pregnancy test at screening visit), women who are currently nursing or lactating, women that have been pregnant within 2 years.
4. Subjects with neuropathy, chronic pain, diabetes mellitus, or taking benzodiazepines or pain medications on a daily basis.

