Study Visit 1: The participant will report to the CRU or Piedmont Plaza 2. The participant will review and sign the Informed Consent. After informed consent is adequately obtained, a detailed medical history will be obtained from the participant, female participants will provide a urine sample to determine pregnancy status. The research nurse will train the participants to estimate pain quantitatively using a 2 cm² Peltier controlled thermode (TSA®) applied to a forearm with 5 sec presentation of stimuli at 39, 41, 43, 45, 47, 49, and 50°C, using a 11 point numerical verbal scale (NRS) anchored at 0 for no pain and 10 for the worst pain imaginable . Typically, the participant is exposed to temperatures between 38° and 51° C using a random staircase method. After this training, we will ask them to report pain intensity on the 0-10 NRS scale every minute for 5 minutes upon exposure to a 4 cm² Peltier controlled thermode at 45°C to the lateral calf. Finally, the subject will place the palmar aspect of the wrist of their dominant hand on a device and report when they first perceive a sensation as the intensity of vibration at a fixed frequency of 256 Hz is slowly increased. We have found

this training session significantly reduces anxiety and variability in pain and hypersensitivity ratings on subsequent study days.

Ultraviolet-B light exposure will be controlled by a commercially available solar simulator and dose control system that meets specifications for FDA sunscreen testing (Solar Light Co., Inc). The solar simulator consists of a 150-watt xenon bulb that produces the full range of solar ultraviolet energy (290-400 nm) without exposing subjects to thermal energy. Exposure is limited to a 3 cm² diameter circle of skin and, after an individualized determination of dose, produces moderate erythema that is sensitive to thermal and mechanical stimulation. During this visit three areas of skin on the subject's calf will be exposed to ultraviolet light for different lengths of time not to exceed 200 seconds. This procedure is not painful, and this burn does not produce spontaneous pain as the burn injury resolves over the next several days.

Study Visit 2

The subject will return to the CRU or Piedmont Plaza 2 24 hours later and the exposed areas evaluated for UV-induced erythema. The purpose of this procedure is to determine each subject's MED, defined as the dose of UV light that produces clear redness with sharply demarcated borders.

Study Visit 3

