The subject will report to the CRU or Piedmont Plaza 2 at least 5 days after study visit 2. After determination of vibration frequency perception threshold on the dominant arm volar aspect of the wrist, the center of the volar aspect of the wrist will be irradiated with an ultraviolet exposure of 2 times the subject's MED. Subjects will be instructed that they can take acetaminophen as needed, but not NSAIDs, over the next 2 days, but that they should not take acetaminophen within 6 hours of study visits 4 and 5.

Study Visit 4

The subject will report to the CRU the day after Study Visit 3. Baseline blood pressure, heart rate and respiratory rate will be measured. Baseline measures will be obtained to include 5 minute presentation of a 45°C stimulus to the lateral calf, perception threshold of vibration intensity on the dominant arm site of ultraviolet burn, and pain threshold using application of calibrated von Frey filaments to the site of ultraviolet burn. Finally, we will map the area of hypersensitivity surrounding the burn

site using a 225mN von Frey filament. Following baseline measurements we will apply the Peltier controlled thermode to the burn site and increase the probe temperature to 40°C for 5 min. Immediately after removing the probe the subject will receive an intramuscular injection of oxytocin (Pitocin®), 10 IU or the same volume (1 ml) of saline. Thresholds to perception of vibration and pain within the area of UV burn and areas of hypersensitivity surrounding the burn area will be determined 5 minutes, 45 minutes, and 65 minutes after injection. A vibratory threshold will also be determined at 30 minutes after the injection. Pain report to a 5 minute presentation of the 45°C stimulus to the lateral calf will be determined at the 20 and 60 min time period after injection. The area of the burn site will be heated to 40°C for 5 min a second time, 40 min after the first.

Study Visit 5

All procedures from Study Visit 4 will be repeated with the cross-over study drug solution.

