Safety and Monitoring: Given that oxytocin is available over the counter in much larger systemic doses than proposed in this application and since multiple scientific reports have examined much larger systemic doses than in this application using only subjective reporting, we propose to only request subjects to report any unusual sensations and query them at the end of each drug administration study day if they experienced any unusual sensations. UV protective glasses will be worn by study staff administering the UV exposure. The subject will be shielded with a barrier so there will be no exposure to their eyes.

Blood pressure, heart rate and respiratory rate will be measured on study visits 4 and 5 at baseline and then at 30 and 60 minutes after the injection.

RISKS

Risks of intramuscular injection include pain and bruising. Risks from the FDA approved heat stimulus device are pain, and the subject can stop testing at any time if the pain they perceive is such that they do not want to continue. Please note that these devices are used in many pain clinics routinely and have multiple fail-safe designs to

avoid thermal burn. Risks from the non-regulatory vibratory device are related only to microshock and are addressed in the Appendix. Risks from the Electromechanical Risks from the UV radiation causes mild sunburn, and may blister or hurt for a few days. The sunburned skin will almost always tan in normal individuals, and may tan more darkly than the surrounding skin for several weeks to several months. It is possible that the darker patches of skin may be present for up to a year. Long-term darkening (discoloration) or scarring is possible, but rare in people with normal skin and a history of normal tanning. Repeated exposure of the skin to UV light is known to produce photoaging (aging of the skin in response to sunlight) and carries the risk of photo carcinogenesis (skin cancer). However, the few exposures in this study, equivalent perhaps to one hour of casual sun exposure during the summer, produces an insignificant increase in lifetime risk.

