Risks of oxytocin are primarily restricted to uterine contraction in the presence of pregnancy, since oxytocin receptors are not present in the non-pregnant uterus (Package insert attached). Additionally there is the possibility of a feeling of being flushed, headache and increased heart rate with no significant change in blood pressure during or immediately after the infusion. These events have been reported by previous participants but were short lived, lasting approximately 12-15 minutes.

Data Safety Monitoring Plan

Although the use of oxytocin in this protocol is outside FDA approval for oxytocin administration during the postpartum period, the dose to be studied is similar to or less than that of multiple recent studies in healthy volunteers with intranasal oxytocin purchased over the counter in the US [10; 12-15; 17; 20-22; 25-32] and without description of adverse events. For these reasons, we do not propose a data safety monitoring committee or special safety evaluation beyond those required by IRB regulations.

Minority, Gender, and Children Participation

Both sexes and races and ethnicities will be actively recruited in this small study. Children under age 18 are not included in these protocols because this protocol because the safety of this product has not been established in children.

Volunteer Payment

Participants will be paid a total of \$500 according to the following payment schedule which we have used throughout the last 2 cycles of this grant's protocols. We believe that this payment schedule is fair and appropriate, paying for each procedure attempted and an additional payment for completion of the entire study.

Completion of study visit 1: \$50

Completion of study visit 2: \$25

Completion of study visit 3: \$25

Completion of study visit 4: \$50

Completion of study visit 5: \$350

Long-term Follow-up

Volunteers will be contacted daily within the following week after the last study visit and questioned about adverse events from the study.

STATISTICAL RATIONALE

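### The only pregnancy test described is at Visit 1, at least 7 days before the first injection and with no stated maximum, so a pregnancy that becomes detectable later would not be found before dosing

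*Combined protocol and SAP*

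**What the plan says.** Exclusion Criteria, item 3, bars pregnant women and gives the check as a "positive result for urine pregnancy test at screening visit". Under Study Visit 1, "female participants will provide a urine sample to determine pregnancy status". No other urine sample is described.

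Visit 2 is 24 hours after Visit 1. For Visit 3, "The subject will report to the CRU or Piedmont Plaza 2 at least 5 days after study visit 2"; Visit 4, with the first injection, is the following day. Before that injection, "Baseline blood pressure, heart rate and respiratory rate will be measured", followed by sensory baselines and heating of the burn site. For Visit 5, "All procedures from Study Visit 4 will be repeated with the cross-over study drug solution". Safety and Monitoring adds only repeat vital signs ("Blood pressure, heart rate and respiratory rate will be measured on study visits 4 and 5 at baseline", then at 30 and 60 minutes) and questions about unusual sensations. The Data Safety Monitoring Plan states that "we do not propose a data safety monitoring committee or special safety evaluation beyond those required by IRB regulations".

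Two other passages bear on the point. Inclusion Criteria, item 4, requires highly effective contraception or abstinence, with a one-cycle minimum counted back from study drug administration. Randomized Treatment limits its reassurance about dose: "In the absence of pregnancy or the postpartum period, doses of oxytocin much greater than this" are said to be free of physiologic adverse effects. Risks gives uterine contraction in pregnancy as the principal hazard.

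**The concern.** The plan's safety argument depends on the subject not being pregnant, yet pregnancy status is checked a week or more before dosing and not again. Blood pressure, by contrast, is re-measured on each dosing day. General Methods gives both treatments to every subject, so each woman receives oxytocin at Visit 4 or Visit 5.

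Two kinds of pregnancy could pass through: one conceived too shortly before Visit 1 to show on that test, and one conceived after Visit 1 when the gap is long enough for it to become detectable. Contraception lowers the chance of either but detects neither. What is at stake is the safety of healthy volunteers who have no expected benefit to set against the risk. The trial's estimates are not affected.

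**Working it through.** The plan gives no figure to reproduce. The check is schedule arithmetic, followed by a probability under declared assumptions.

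**Test-to-injection gap** (Study Visits 1 to 5). Take Visit 1 as day 0.

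- Visit 2: day 1.
- Visit 3: day 1 + 5 = 6 or later, with no upper limit.
- Visit 4: day 6 + 1 = 7 or later.
- Visit 5: day 7 + 1 = 8 or later.

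The test therefore precedes the first injection by at least 1 + 5 + 1 = 7 days and the second by at least 8.

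**Which conceptions a Visit 4 test would add.** Let L be the days from conception to a positive urine test; the documents give no value, and 7 to 14 is assumed. The Visit 1 test covers conceptions up to day −L, and a Visit 4 test covers them up to day (gap − L). The repeat test thus adds as many days of conceptions as the gap is long, of which max(0, gap − L) fall after Visit 1.

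| Gap (days) | Days after Visit 1: L = 7 | L = 10 | L = 14 |
|---|---|---|---|
| 7 | 0 | 0 | 0 |
| 14 (assumed) | 7 | 4 | 0 |
| 30 (assumed) | 23 (77%) | 20 (67%) | 16 (53%) |

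At the 7-day minimum the whole gain is conceptions just before Visit 1. At 30 days, 53% to 77% of it is conceptions after Visit 1.

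**Probability per woman.** With an assumed annual contraceptive failure rate f, constant over the window, P = 1 − (1 − f)^(gap/365).

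| Gap (days) | f = 1% | f = 5% | f = 15% |
|---|---|---|---|
| 7 | 0.019% | 0.098% | 0.311% |
| 14 | 0.039% | 0.197% | 0.621% |
| 30 | 0.083% | 0.421% | 1.327% |

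Example: 1 − 0.85^(7/365) = 0.00311.

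**Probability that anyone is affected.** Statistical Rationale refers to 5 remaining subjects, whose sex is not stated. The equal split in General Methods applies to all ten, so 0 to 5 of the remaining subjects are women. With 5 women and a 7-day gap, 1 − (1 − P)^5 gives 0.096%, 0.491% and 1.546% for f = 1%, 5% and 15%.

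**The case against.** The strongest reply is that the main control is already tied to dosing. Inclusion 4 counts its one-cycle minimum back from study drug administration, so it is meant to cover the days between test and injection and those just before Visit 1. At the 7-day minimum, all the gain from a repeat test lies in that period. The upper figures also combine unfavourable assumptions: 15% failure despite a requirement for highly effective methods, and five fertile women among five subjects. With 2 to 3 women and 1% to 5% failure, the 7-day figure that anyone is affected is 1 − (1 − 0.00019)^2 ≈ 0.04% to 1 − (1 − 0.00098)^3 ≈ 0.29%. Long gaps are permitted but not shown to occur, and they give a woman more time to recognise and report a pregnancy herself. The documents do not quantify harm from one 10 IU dose in early pregnancy. The safety plan keeps whatever the IRB requires, and a repeat test might be stated in the consent pages or Appendix, which are not in the supplied text.

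Most of this stands, and it keeps the point small. It does not remove it: contraception prevents pregnancy but does not detect it, and the only check the plan describes is at screening. Because double-barrier methods are allowed, the higher failure rates cannot be dismissed altogether.

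Testing at Visit 3 would avoid irradiating a woman who then tests positive. It is one day further from dosing, so at the minimum gap it would add 6 days of conceptions instead of 7.

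**Conclusion.** The concern holds as a low-probability gap worth closing, not as a failed safeguard. The schedule facts are certain on the supplied text: one test, at least 7 days before the first injection and 8 before the second, no maximum, and no repeat listed.

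The size is about 0.02% to 0.31% per woman of child-bearing potential at the 7-day minimum, and at most 0.10% to 1.5% that at least one of five women is affected. Lower failure rates are the more plausible, given the contraception rule. These probabilities rest wholly on the assumed failure rates; the split between conceptions before and after Visit 1 also rests on the assumed detection lag. The descriptive analysis is unaffected.

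**What to change.** Keep the Visit 1 test and inclusion 4. At Visit 4, alongside the baseline vital signs and before the first injection, repeat the urine test in the women to whom inclusion 4 applies: those of child-bearing potential or less than a year past menopause. Do this whatever the treatment order, so that the blind is preserved, and let the result cover Visit 5 the next day. Reword exclusion 3 so that a positive urine test either at screening or before study drug administration excludes the subject.

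The cost is 0 to 5 further dipsticks of a kind already in use, a few minutes each, and a short amendment. A woman who tests positive at Visit 4 will already have been irradiated at Visit 3 and would need replacing. The allowance of 12 enrolled for 10 evaluable leaves at most 12 − 10 = 2 spare places, and the plan does not say how many are used. The repeat test still misses a conception too recent to detect at Visit 4, so contraception remains the main safeguard.

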In order to determine the threshold for perception of vibration, we have created a simple device that produces an oscillatory / vibratory stimulus which can be used on the skin. The subject places the area of interest on the device and the device is set to slowly increase the intensity of vibration at 256Hz until the subject first perceives this. This is repeated twice in the areas of interest. More details on the device are provided in the Appendix.

We anticipate that oxytocin will have no effect on normal A β fibers with testing in normal skin but will decrease the detection threshold for vibration intensity towards normal in the area of UV radiation exposure .

TEST OF A δ FIBER SENSITIVITY

[figure not shown]
Pain threshold to punctate stimulation within the area of irradiation will be determined using calibrated von Frey filaments and an up-down sequential method which efficiently estimates median thresholds [7].

SECONDARY OUTCOME MEASURE: SUSTAINED HEAT

As part of a protocol used by us in several studies, the surface of the skin of the forearm opposite to the area of irradiation is heated to 45°C using an FDA approved, Peltier-controlled thermode for a period of 5 minutes (TSA®, Medoc, Ramat Yishai, Israel). This typically results in a slowly increasing pain experience, peaking at 5 minutes in the mild to low moderate range and has been tolerated by more than 150 subjects in studies over the past 14 years.

In an interim analysis of an ongoing clinical study in volunteers, we noted that spinal injection of oxytocin, 15 µg (equivalent to 9 IU), that pain from this sustained heat was dramatically reduced over the 5 minutes of stimulus presentation (figure). In contrast, spinal oxytocin had no effect on the stimulus-response relationship of pain to noxious heat over a 42-50°C range when the stimuli were presented for only 5 seconds. These data suggest that oxytocin reduces C-fiber mediated signaling of sustained heat pain, likely through a spinal site of action.

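### The first heart rate after injection, at 30 minutes, comes too late to record an early rise of the 12-15 minute length that the protocol lists as a risk

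*Combined protocol and SAP*

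**What the plan says.** The Safety and Monitoring section has blood pressure, heart rate and respiratory rate "measured on study visits 4 and 5 at baseline and then at 30 and 60 minutes after the injection". Study Visit 4 repeats the baseline measurement and schedules no earlier reading after injection; Study Visit 5 repeats Visit 4 with the other treatment.

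The Risks section names flushing, headache and "increased heart rate with no significant change in blood pressure during or immediately after the infusion" as possible effects of oxytocin. It adds: "These events have been reported by previous participants but were short lived, lasting approximately 12-15 minutes". The study, route and dose behind that experience are not given. In this trial oxytocin is a single 1 ml intramuscular injection of 10 IU.

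Other observation is planned. Subjects are asked to report unusual sensations, and staff will "query them at the end of each drug administration study day if they experienced any unusual sensations". The Long-term Follow-up section adds daily contact in the week after the last visit. Staff are also with the subject for testing before 30 minutes. Thresholds and the area of sensitivity "surrounding the burn area will be determined 5 minutes, 45 minutes, and 65 minutes after injection", and the pain report to the 45°C "stimulus to the lateral calf will be determined at the 20 and 60 min time period after injection".

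**The concern.** The protocol describes a heart rate effect that comes on with, or straight after, dosing and is over in about a quarter of an hour. It then takes its first heart rate after injection at twice that interval. If the effect follows the injection as described, the schedule cannot show it. Normal values at 30 and 60 minutes could then be read as showing no heart rate effect, which they cannot do for an early one.

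The stake is the quality of the safety data, not the main results. Heart rate is not an outcome, and the Statistical Rationale proposes descriptive statistics for sensory measures. That section also says the pilot is to inform a grant application for intravenous infusions of oxytocin, so early paired readings on oxytocin and saline days would help in planning monitoring for that study.

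**Working it through.** The protocol gives no figure to reproduce. The check is whether a scheduled reading falls inside an episode.

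**Inputs**
- Readings after injection: 30 and 60 minutes (Safety and Monitoring).
- Episode length D: 12 to 15 minutes (Risks, stated for infusion and for the listed events together). Applying it to heart rate after an intramuscular injection is an assumption.
- Onset s, in minutes after injection: not given for this route, so varied from 0 to 30. No distribution of onset is assumed.

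**Rule.** An episode is seen at reading r if s ≤ r ≤ s + D. Reading r therefore covers onsets from r − D (or 0, if that is negative) up to r.

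**Present schedule**
- D = 12: the 30-minute reading covers onsets from 30 − 12 = 18 to 30. Onsets before 18 minutes are missed.
- D = 15: it covers onsets from 30 − 15 = 15 to 30. Onsets before 15 minutes are missed.
- An episode starting at injection ends at 12-15 minutes, which is 15-18 minutes before the first reading.

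**Added readings: onsets covered within 0-30 minutes**

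| Readings (min) | D = 12 | D = 15 |
|---|---|---|
| 12, 30 | 0-12 and 18-30; misses between 12 and 18 | 0-12 and 15-30; misses between 12 and 15 |
| 10, 18, 30 | 0-10, 6-18, 18-30; none missed | 0-10, 3-18, 15-30; none missed |
| 12, 18, 30 | 0-12, 6-18, 18-30; none missed | 0-12, 3-18, 15-30; none missed |

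**Tolerance, for D = 12**
- First reading at 14 instead of 12: it covers onsets from 14 − 12 = 2, so onsets in the first 2 minutes are lost.
- Second reading at 17 instead of 18: it covers onsets only up to 17, and the 30-minute reading begins at 18, so onsets between 17 and 18 are lost.

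**Number of readings.** The Statistical Rationale puts the subjects still to be studied at five. Two readings × 2 drug days × 5 subjects = 20, of which 10 fall on oxytocin days. One reading gives 1 × 2 × 5 = 10.

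**The case against.** The strongest objection is that the mismatch rests on a borrowed figure. The Risks section speaks of an infusion, this trial gives an intramuscular injection, and the 12-15 minutes describes flushing, headache and heart rate together. If onset after injection is slower, at 15-18 minutes or later, the 30-minute reading would catch it. This stands as a limit on certainty. It does not remove the point, because the statement sits in this protocol's own risk section and nothing there says that onset is later by this route.

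Second, light monitoring was chosen with reasons given: larger systemic doses have been studied with subjective reporting alone, and the Data Safety Monitoring Plan declines special safety evaluation. That explains why little is measured. It does not explain why the readings that are taken should fall after the window of the listed effect. Self-report may pick up symptoms, but it cannot supply a heart rate, and a rise may go unfelt.

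Third, the remedy has weaknesses. A reading between a punctate pain test and a heat test may be altered by pain or anticipation. The tests begun at 5 minutes may run past 12 minutes, which would lose the earliest onsets of a 12-minute episode. Staff who see a rise may guess the treatment before the later co-primary tests at 30, 45 and 65 minutes. Only 10 of the 20 added readings would be on oxytocin, and no threshold for a rise is set. All of this is fair. The saline day gives a within-subject comparison under the same test sequence, and the 30-minute reading already carries some of the unblinding risk. Even so, the added data would describe early heart rate in a few subjects rather than settle the question.

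**Conclusion.** The concern holds, as a minor point of design. Under the present schedule no heart rate is recorded for an episode that starts less than 15 minutes (if it lasts 15) or less than 18 minutes (if it lasts 12) after injection. The readings therefore cannot confirm or rule out an early rise of the kind the protocol lists.

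This rests on carrying the 12-15 minute duration from infusion to intramuscular injection, and on a rise being recognisable from a single reading while it lasts. How likely an early onset is by this route cannot be judged from the protocol.

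The safety consequence is small. Subjects are of physical status I with "resting heart rate 45-100 beats per minute" at entry, the events are described as short lived, and clinical observation is not absent. What is missing is a recorded value before 30 minutes.

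**What to change.** On visits 4 and 5, add a heart rate at 10-12 minutes, after the 5-minute sensory tests, and another at 18 minutes, before the 20-minute heat test. If only one is acceptable, take it at 12 minutes. If the sensory tests run past 12 minutes, take the reading as soon as they end and note the actual time.

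A pulse alone is enough at 18 minutes, since the Risks section reports no significant change in blood pressure. Avoiding a cuff there also keeps the arm clear for the heat test: the section on sustained heat says that "the surface of the skin of the forearm opposite to the area of irradiation is heated", although Study Visit 4 places the test on the lateral calf. Blood pressure at 10-12 minutes is optional, with the cuff on the arm without the burn. Record values without comment to the subject.

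The cost is 20 brief readings for the five subjects still to be studied (10 with the single reading), taken by staff already present, and a small change to the protocol. Nothing is added before the 5-minute co-primary tests. Two downsides remain: a small chance that a visible rise hints at treatment before the later tests, and no early readings for subjects already studied.

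### Pregnancy is tested only at Visit 1, at least 7 days before the first injection and with no upper limit; a repeat urine test should be added at Visit 4 before dosing

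*Combined protocol and SAP*

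**What the plan says.** The RISKS section identifies the setting in which the drug is hazardous: "Risks of oxytocin are primarily restricted to uterine contraction in the presence of pregnancy". Three safeguards follow from this.

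- **Contraception.** Under Inclusion Criteria, item 4, women of child-bearing potential, and those less than 1 year past menopause, "must be practicing highly effective methods of birth control" or be abstinent, for at least one full cycle before study drug.
- **Exclusion.** Exclusion Criteria, item 3, removes pregnant women, identified by a "positive result for urine pregnancy test at screening visit", as well as nursing women and those pregnant in the previous 2 years.
- **Test.** At Study Visit 1, "female participants will provide a urine sample to determine pregnancy status".

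On timing, Visit 2 is 24 hours after Visit 1. Visit 3 is "at least 5 days after study visit 2". For Visit 4 the protocol says "The subject will report to the CRU the day after Study Visit 3", and Visit 5 falls on the following day. At Visit 4, after baseline tests and heating of the burn site, "Immediately after removing the probe the subject will receive an intramuscular injection of oxytocin" or of saline. Visit 5 repeats these procedures with the other solution.

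The safety measures listed for the dosing days are vital signs ("Blood pressure, heart rate and respiratory rate will be measured on study visits 4 and 5 at baseline" and twice after injection) and questions about unusual sensations. The text for Visits 2 to 5 mentions no further pregnancy test.

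**The concern.** The protocol's reassurance about safety depends on the woman not being pregnant when she is dosed. RANDOMIZED TREATMENT makes its statement about higher doses conditional on there being no pregnancy, and the Data Safety Monitoring Plan proposes no special safety evaluation beyond what the IRB requires. That condition is checked once, at screening, and not on the day it matters.

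The safeguards are also tied to different dates. The contraception rule counts back from study drug administration, while the test is fixed to screening. Because the interval from Visit 2 to Visit 3 has only a lower limit, the test can be of any age when oxytocin is given.

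A pregnancy too early to detect at Visit 1 could be detectable by Visit 4, and no listed procedure would find it before a 10 IU injection. The participants are healthy volunteers with no therapeutic benefit to set against an avoidable exposure.

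**Working it through.** The plan gives no figure to reproduce, so the check is the age of the test at dosing and then the number of exposures a repeat test could prevent.

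**Age of the test.** Take Visit 1 as day 0.

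| Visit | Interval in the protocol | Earliest day |
|---|---|---|
| 1 (urine test) | – | 0 |
| 2 | 24 hours after Visit 1 | 1 |
| 3 | at least 5 days after Visit 2 | 1 + 5 = 6 |
| 4 (first injection) | day after Visit 3 | 6 + 1 = 7 |
| 5 (second injection) | day after Visit 4 | 7 + 1 = 8 |

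Depending on the randomized order, oxytocin is given at least 7 or at least 8 days after the test. No maximum follows from the text.

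**Assumptions not in the documents.**
- Annual pregnancy rate r on the accepted methods: 1% to 15%.
- Gap g from the Visit 1 test to Visit 4: 7 days (the protocol minimum) to 28 days (assumed).
- Period b after conception in which a urine test is negative: 14 days.
- Every woman enrolled can conceive. This is an upper limit, because the age range runs to under 60.

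**Number of women n.** GENERAL METHODS plans equal numbers of men and women, ten in total, so n = 5 (6 if all 12 permitted subjects enrol). STATISTICAL RATIONALE refers to 5 remaining subjects. Their sex is not stated; an even split gives n = 2 to 3.

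**What a repeat test adds.** The Visit 1 test misses conceptions after day −14. A Visit 4 test misses those after day g − 14. The repeat test therefore picks up exactly g further days of conceptions. Of these, max(0, g − 14) days fall after Visit 1: none at g = 7, and 14 at g = 28. On the minimum schedule, all the extra pregnancies found would have begun before Visit 1.

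**Exposures prevented** = n × r × g/365.
- Five women: 5 × 0.01 × 7/365 = 0.001, to 5 × 0.15 × 28/365 = 0.058.
- Two to three women: 2 × 0.01 × 7/365 = 0.0004, to 3 × 0.15 × 28/365 = 0.035.
- Six women, upper end: 6 × 0.15 × 28/365 = 0.069.

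**All undetected pregnancies at the first injection under the current plan** = n × r × (g + 14)/365.
- Five women: 5 × 0.01 × 21/365 = 0.003, to 5 × 0.15 × 42/365 = 0.086.

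**Share caught by the repeat test** = g/(g + 14).
- g = 7: 7/21 = 33%.
- g = 28: 28/42 = 67%.

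**Still missed** = n × r × 14/365.
- Five women: 5 × 0.01 × 14/365 = 0.002, to 5 × 0.15 × 14/365 = 0.029.

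If oxytocin falls on Visit 5, the Visit 4 test is one day old. The number prevented does not change, and the upper figure still missed becomes 5 × 0.15 × 15/365 = 0.031.

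**The case against.** The strongest objection concerns weight. The main control is already in place: effective contraception or abstinence for a full cycle before dosing, a screening test and a 2-year exclusion. On the minimum schedule the repeat test would find only conceptions 14 to 21 days before dosing. With a cycle of about 28 days (assumed) these fall inside the required contraception period, so each would be a contraceptive failure or non-compliance. The counts are exposures, not harms, and nothing in the documents shows that a single 10 IU dose is harmful that early. The upper figures combine several unfavourable assumptions, including a 15% failure rate despite the contraception requirement. The point does not touch the outcomes or the descriptive analysis.

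Most of this stands, and it is why the benefit is called small and the test a precaution. It does not remove the point. Contraception lowers the chance of pregnancy but does not verify status, and the protocol already accepts this by testing at Visit 1 despite requiring contraception. The lower figures use a 1% rate and the shortest gap, but the protocol does not limit the gap.

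A repeat test might also be required in the consent form or by the IRB, neither of which is available here. That is possible, so the claim is only that the protocol lists no repeat test. If one is already done, writing it into Visit 4 costs nothing.

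**Conclusion.** The concern holds. The only pregnancy test listed is at least 7 days old at the first injection and at least 8 days old at the second, with no upper limit, although pregnancy is the risk setting the protocol itself names. This part follows from the visit schedule alone.

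The size of the benefit rests on the assumed pregnancy rate, gap and undetectable period, and it is well below one exposure on any of them. A repeat test would remove a third to two thirds of the otherwise undetected pregnancies at first injection and leave the most recent conceptions undetected. Whether an exposure this early does harm cannot be judged from the documents. The change should be made because it is a near-free protection for healthy volunteers; the validity of the results does not depend on it.

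**What to change.** Add to Study Visit 4: on arrival, before any study drug, repeat the urine pregnancy test in every woman covered by Inclusion Criteria, item 4, and do not inject if it is positive. Word Exclusion Criteria, item 3, to match, so that a positive result at Visit 4 also excludes. One test serves both injections because Visit 5 is the next day. Keep the contraception requirement, since no urine test detects the most recent conceptions.

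The cost is one test per eligible woman, of a kind the trial already uses, at a visit already held in the research unit. That is at most 5 tests, 6 if 12 subjects enrol, or about 2 to 3 among the remaining 5 subjects if they split evenly by sex. Schedule, outcomes and analysis are unchanged.
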